**16.2. DEATHS**

If any subjects die during the study as recorded on the Death eCRF (DTH), the information is to be presented in a data listing.

---

**16.3. LABORATORY EVALUATIONS**

Results from the central laboratory are to be included in the reporting of this study for Haematology, Biochemistry, Urine dipstick and Immunology. Quantitative laboratory assessments are to be summarised by descriptive statistics and presented in International System of Units (SI). Categorical assessments are to be presented by frequency (n) and percentage (%) of subjects.

---

Document: TH005 SAP Version 2.docx

Author: [name]

Version Number:

2.0

Version Date:

24MAR2017

Template No: CS\_TP\_BS016 – Revision 3

Effective Date: 01May2012

Reference: CS\_WI\_BS005

Copyright © 2012 Quintiles Transnational Corp. All rights reserved.

The contents of this document are confidential and proprietary to Quintiles Transnational Corp. Unauthorized use, disclosure or reproduction is strictly prohibited.

---

Quantitative laboratory assessments reported as “< X”, i.e. below the lower limit of quantification (BLQ), or “> X”, i.e. above the upper limit of quantification (ULQ), are to be converted to X for the purpose of quantitative summaries, but are to be presented as recorded, i.e. as “< X” or “> X” in the listings.

The following summaries are to be provided for laboratory data:

- Actual and change from Baseline by visit (for quantitative measurements)
- Shift from Baseline according to normal reference range criteria (for quantitative measurements and categorical measurements) by visit
- Listings of all laboratory assessments

The following assessments are to be measured and presented:

- Haematology: Haematocrit, haemoglobin, red blood cells, white blood cells (WBC), WBC differentials (neutrophils, eosinophils, basophils, lymphocytes, monocytes) and platelets
- Biochemistry: Sodium, potassium, chloride, urea, creatinine, calcium, phosphorus, total protein, albumin, uric acid, total bilirubin, glucose (random), lactate dehydrogenase, creatine phosphokinase, alanine transaminase, aspartate transaminase, gamma glutamyltransferase and alkaline phosphatase
- Urine dipstick: pH, protein, ketones, blood and glucose
- Immunology: All relevant perennial allergen specific IgE
- Tryptase for anaphylactic response

Blood sample for tryptase is only to be taken in the event of a suspected anaphylactic reaction. The initial sample should be taken approximately 1 hour after the reaction, with a further sample at approximately 3 hours and then repeated every 3 hours until the Investigator is satisfied that the subject may be discharged. Tryptase laboratory results are to be listed separately.

### **16.3.1. LABORATORY REFERENCE RANGES AND ABNORMAL CRITERIA**

Quantitative laboratory assessments are to be compared with the relevant laboratory reference ranges in SI units and categorised as:

- Low: Below the lower limit of the laboratory reference range
- Normal: Within the laboratory reference range (upper and lower limit included)
- High: Above the upper limit of the laboratory reference range
- Normal/Abnormal results and clinical significance as reported by the investigator is only to be presented in data listings.

---

Document: TH005 SAP Version 2.docx  
Author: [name]

Version Number: 2.0  
Version Date: 24MAR2017

Template No: CS\_TP\_BS016 – Revision 3  
Effective Date: 01May2012

Reference: CS\_WI\_BS005

Copyright © 2012 Quintiles Transnational Corp. All rights reserved.  
The contents of this document are confidential and proprietary to Quintiles Transnational Corp. Unauthorized use, disclosure or reproduction is strictly prohibited.

---

## 16.4. ANTIBODIES TO PANEL OF DER P ALLERGES

At Consent Visit 1A a blood sample is to be taken for measurement of levels of IgE antibodies to a fixed panel of Der p allergens, using an immune-affinity based analysis technology such as ImmunoCAP®.

Observed values are to be summarised by descriptive statistics and treatment group for each panel.

Specific IgE for allergen components will be summarised as number of subjects with positive (three grade categories) vs negative (<0.3 kU/L) results for all allergen components.

Positive results will be divided in the three grade categories as described below for specific IgE values.

- Low:  $\geq 0.3 - < 1$  kU/L
- Moderate/high:  $\geq 1 - < 15$  kU/L
- Very high:  $\geq 15$  values kU/L

## 16.5. VITAL SIGNS

The following vital signs assessments are to be taken rested and in the sitting or semi-recumbent position and reported for this study:

- Systolic Blood Pressure (mmHg)
- Diastolic Blood Pressure (mmHg)
- Pulse Rate (bpm)
- Respiratory Rate (breaths/min)
- Oral body temperature (°C)
- At each medication administration visit (Visit 3A to Visit 3H), vital signs are to be taken pre-dose as well as 30 minutes post-dose.

The following summaries are to be provided for vital signs data by descriptive statistics and treatment group for each visit:

- Actual and change from Baseline/pre-dose observation by visit
  - For medication administration visits (Visit 3A to Visit 3H), change from pre-dose to 30 minutes post-dose observation is to be presented
  - For all other visit assessments (including the pre-dose assessment at Visit 3A to Visit 3H), change from Baseline is to be presented

---

Document: TH005 SAP Version 2.docx  
Author: [name]

Version Number: 2.0  
Version Date: 24MAR2017

Template No: CS\_TP\_BS016 – Revision 3  
Effective Date: 01May2012

Reference: CS\_WI\_BS005

Copyright © 2012 Quintiles Transnational Corp. All rights reserved.  
The contents of this document are confidential and proprietary to Quintiles Transnational Corp. Unauthorized use, disclosure or reproduction is strictly prohibited.

---

- Listing of all vital signs data

#### **16.5.1. VITAL SIGNS SPECIFIC DERIVATIONS**

Body temperature assessments recorded in Fahrenheit ( $^{\circ}\text{F}$ ) are to be converted to Celsius ( $^{\circ}\text{C}$ ) as follows:

- $^{\circ}\text{C} = (^{\circ}\text{F} - 32) \times \frac{5}{9}$

### **16.6. PHYSICAL EXAMINATION**

At Screening subjects are to undergo a full examination comprising of:

- Eye, ears, nose, throat, neck, including a check for nasal polyps
- Respiratory system
- Central and peripheral nervous system
- Cardiovascular system
- Gastrointestinal system (including the mouth)
- Musculoskeletal system
- Skin
- Lymph node palpation
- Other systems if abnormality is suspected

At Visit 3I and Visit 5 targeted physical examinations are to be performed with organ systems examined if the medical history or AEs of a subject indicate a reason for examination.

Shift from Screening to Visit 3I and Visit 5 in physical examination finding (Normal, Abnormal, Not Done) is to be presented by organ system and treatment group.

Abnormal physical examination findings are to be listed.

### **16.7. OTHER SAFETY ASSESSMENTS**

#### **16.7.1. FORCED EXPIRATORY VOLUME IN 1 SECOND (FEV1)**

The FEV1 is to be measured at Screening, prior to and 30 minutes post study medication administration (Visits

---

Document: TH005 SAP Version 2.docx  
Author: [name]

Version Number: 2.0  
Version Date: 24MAR2017

Template No: CS\_TP\_BS016 – Revision 3  
Effective Date: 01May2012

Reference: CS\_WI\_BS005

Copyright © 2012 Quintiles Transnational Corp. All rights reserved.  
The contents of this document are confidential and proprietary to Quintiles Transnational Corp. Unauthorized use, disclosure or reproduction is strictly prohibited.

3A-3H), at the End of Dosing Assessment (Visit 3I), and at the end of the PAC1 (Visit 4B), PAC2 (Visit 4D) and PAC3 (Visit 4F) periods.

At each assessment  $FEV_1$  is to be measured according to the American Thoracic Society guidelines with the subject sitting and the highest reading is to be recorded in the eCRF.

Absolute and change from Baseline/pre-dose values of  $FEV_1$  is to be summarised by descriptive statistics and treatment group for each visit.

- For medication administration visits (Visit 3A to Visit 3H), change from pre-dose to 30 minutes post-dose observation is to be presented
- For all other visit assessments (including the pre-dose assessment at Visit 3A to Visit 3H), change from Baseline is to be presented
- $FEV_1$  data is to be listed
- An additional listing is to be created for any reduction in  $FEV_1$  of more than 20% from Baseline/pre-dose, as well as a reduction of more than 30% from Baseline/pre-dose
  - The frequency (n) and percentage (%) of subjects with a reduction of more than 20% from Baseline/pre-dose as well as a reduction of more than 30% from Baseline/pre-dose is to be presented by treatment group at each applicable visit.  
Percentages are to be calculated relative to the total number of subjects in the analysis population with data available.

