### 5.5.1 Dose Reduction

In the event that a subject experiences a grade 3 or 4 injection site reaction (see Section 6.2.2.1) or a grade 2 systemic allergic reaction (See Appendix 4) the following dose reduction scheme should be followed:

- On first occurrence of a dose reduction trigger reaction the next dose should be reduced by half. This is achieved by administering a dose of 50  $\mu$ L instead of 100  $\mu$ L.
- If the reduced dose is well tolerated then the subsequent dose should be escalated back to 100  $\mu$ L. If this is well tolerated then further doses should continue to be 100  $\mu$ L.
- If however the full dose is again not well tolerated and a further trigger reaction occurs then the dose should again be reduced to  $50 \,\mu L$  and remain at that dose for the remainder of the study.

VERSION FINAL 4.0 CONFIDENTIAL PAGE 34 OF 92

• If two consecutive half doses are not well tolerated the subject should be withdrawn from the study.

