# 7.5.4 Safety Analysis

Safety will be evaluated by analysis of the following parameters:

- AEs;
- Physical examination;
- Clinical laboratory tests (including immunology);
- FEV1;
- Vital signs;
- Local reactions at the injection site.

The primary safety endpoint will be a comparison of the number of adverse events, and subjects with adverse events, in the HDM-SPIRE groups compared to placebo.

For safety analysis, descriptive statistics such as N, mean, median, minimum, maximum and SD will be summarised by treatment group for continuous variables. Frequency distribution will be summarised for categorical variables. No formal inferential tests will be performed on safety data.

The number and percentage of subjects who experience AEs will be presented by treatment group. Based on the MedDRA Preferred Term, subjects who experience the same AE on multiple occasions will be summarised at the maximum severity and most conservative relationship to the study medication. If 2 or more AEs are reported as a single event, the

VERSION FINAL4.0 CONFIDENTIAL PAGE 74 OF 92

individual terms will be reported as separate AEs.

The total number of AEs will be summarised by MedDRA System Organ Class and Preferred Term for each treatment group. Descriptive statistics will be presented for differences between the HDM-SPIRE treatment groups and the placebo group, but no hypothesis testing is planned.

Any deaths, SAEs and AEs leading to discontinuation of study medication administration will also be summarised by treatment group.

Local reactions at the injection site will be summarised by type of reaction and visit for each treatment group.

Physical examinations data will be listed only.

Vital signs will be presented as descriptive statistics on absolute values and the change from baseline will be summarised for each treatment group by visit.

 $FEV_1$  will be presented as descriptive statistics and the absolute change from baseline and percentage change from baseline will be summarised for each treatment group by visit.

Clinical laboratory data for individual subjects will be listed and any out of range values will be highlighted. Laboratory data will be summarised for each treatment group by visit as follows: summary of absolute values and change from baseline and analysis of shifts from baseline.

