## 6.6. COMMON CALCULATIONS

For quantitative measurements:

- Change from Baseline is to be calculated as
  - Test Value at Visit X – Baseline Value

---

Document: TH005 SAP Version 2.docx  
Author: [name]

Version Number: 2.0  
Version Date: 24MAR2017

Template No: CS\_TP\_BS016 – Revision 3  
Effective Date: 01May2012

Reference: CS\_WI\_BS005

Copyright © 2012 Quintiles Transnational Corp. All rights reserved.  
The contents of this document are confidential and proprietary to Quintiles Transnational Corp. Unauthorized use, disclosure or reproduction is strictly prohibited.

---

- Percentage change from Baseline is to be calculated as
  - $[(\text{Test Value at Visit X} - \text{Baseline Value}) / \text{Baseline Value}] \times 100$
- Descriptive statistics are to include n, mean, standard deviation (SD), median, minimum and maximum

For qualitative measurements (e.g. Gender):

- Summaries are to include frequency (n) and percentage (%) of subjects. Percentages are to be calculated as either
  - The number of subjects within a category relative to the total number of subjects in the relevant analysis population with data available. In this case a missing category is to be added to indicate the number of subjects with no data and the missing counts are not to be included in the denominator for the percentage calculation, or
  - The number of subjects in a category relative to the total number of subjects in the relevant analysis population

The applicable method of percentage calculation is indicated in each relevant analysis section.

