#### **16.7.2. LOCAL REACTION AT INJECTION SITE**

Grading of each of the four components of an injection site reaction (pain, tenderness, induration/swelling and erythema/redness) is to be categorised as 'Grade 0', 'Grade 1', 'Grade 2', 'Grade 3' or 'Grade 4' in accordance with the severity of the reactions as specified in Table 7, Section 6.2.2.1 of the protocol.

Frequency (n) and percentage (%) of subjects with local reactions at the injection site are to be summarised by reaction grade and visit for each treatment group.

All injection site reactions are to be listed.

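### FEV1 falls and injection-site grades are counted only visit by visit, so the plan never gives the share of subjects per regimen who ever had a marked fall, or their worst grade

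*SAP*

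**What the plan says.** **FEV1.** SAP 16.7.1 summarises absolute values and change by visit, lists the larger falls ("An additional listing is to be created for any reduction in" FEV1 beyond 20% or 30%), and counts subjects beyond each threshold; the second count reads "a reduction of more than 30% from Baseline/pre-dose is to be presented by treatment group at each applicable visit". The denominator is stated: "Percentages are to be calculated relative to the total number of subjects in the analysis population with data available". At Visits 3A-3H the change runs from pre-dose to 30 minutes post-dose; at other assessments it runs from Baseline.

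**Injection site.** SAP 16.7.2: "Frequency (n) and percentage (%) of subjects with local reactions at the injection site are to be summarised by reaction grade and visit". All reactions are listed. No denominator is given, although SAP 6.6 describes two methods and says: "The applicable method of percentage calculation is indicated in each relevant analysis section".

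**Protocol.** Section 7.5.4 also works by visit for both outcomes. For FEV1 it requires that "the absolute change from baseline and percentage change from baseline will be summarised for each treatment group by visit".

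**Dosing after a reaction.** Protocol 5.5.1: "On first occurrence of a dose reduction trigger reaction the next dose should be reduced by half". If the half dose is tolerated, the full volume is given again. Protocol 4.6 ends dosing after a grade 3 or 4 systemic reaction, after repeated grade 3 or 4 local reactions despite reduction, or after a related serious event. Protocol 6.2.2.1 allows a dosing visit postponed for low pre-dose FEV1 to become a missed visit.

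**The concern.** Safety and tolerability are a secondary objective (protocol 2.2), and the study is meant to choose a regimen for Phase 3 (protocol 2.0). Protocol 1.3.1 says that 12 nmol is the highest unit dose tested so far and gives equivalent tolerability as part of the reason for the 20 nmol arm. Neither completed study included subjects with asthma (protocol 1.2), who may enter this one.

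The basic quantity for comparing regimens is the proportion of subjects who, at any dose, had an FEV1 fall beyond a threshold or a local reaction of a given grade. A by-visit table does not contain it, because one subject may appear in several columns or in one. Two arms with identical columns may differ widely in the number of people affected.

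A trend across the columns is also hard to read. Late visits differ from early ones in what is injected, in the volume some subjects receive and, to an unknown degree, in who is still dosed. A falling rate could be mistaken for growing tolerance.

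**Working it through.** **1. Plan's own figure.** Neither document gives a rate for FEV1 falls or injection-site reactions, so there is none to reproduce. The rates below are assumptions. The only planned number used is the group size of about 165 (protocol 4.1), with eight dosing visits, 3A-3H.

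**2. From visit rates to subjects.** Let p be the rate at each of k visits, with no missing data. The share of subjects ever affected is
- lowest, if the same subjects react each time: p
- if visits are independent: 1 - (1 - p)^k
- highest, if different subjects react each time: k × p

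| Assumed p | Subjects per column (165 × p) | Ever affected, k = 8: lowest / independent / highest | Ever affected, k = 4: lowest / independent / highest |
|---|---|---|---|
| 1% | 1.7 | 1.0% / 7.7% / 8.0% | 1.0% / 3.9% / 4.0% |
| 2% | 3.3 | 2.0% / 14.9% / 16.0% | 2.0% / 7.8% / 8.0% |
| 5% | 8.3 | 5.0% / 33.7% / 40.0% | 5.0% / 18.5% / 20.0% |

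At p = 2% and k = 8, the same columns fit 165 × 0.02 = 3.3 subjects or 165 × 0.16 = 26.4 subjects. The k = 4 figures apply where only the four active doses matter, as in the 4 x 12 and 4 x 20 nmol arms. The table fixes the per-subject share only to within a factor of k.

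**3. Do other outputs supply the number?**
- SAP 16.1 counts each subject once for any, severe, related and special-interest treatment-emergent events, and for events within 24 hours of a dose. SAP 16.1.1.1 takes the worst severity per preferred term.
- These tables cover only what is reported as an adverse event. Severity is mild, moderate or severe, not the protocol's Grades 0-4, and no FEV1 threshold enters.
- The listings hold the individual values but give no count by arm.

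**4. Are late visits comparable with early ones?**
- In the 4 x 12 and 4 x 20 nmol arms, Visits 3E-3H are placebo injections (SAP 3.1), so a late decline is expected by design.
- A first trigger reaction leads to a half dose and, if that is tolerated, back to the full volume. Most first reactors therefore stay in the later columns.
- An FEV1 fall above 20% or 30% is not in itself a trigger for reduction or stopping in protocol 4.6 or 5.5.1.
- Illustration of depletion, eight equal active doses: assume a susceptible share f = 10%, risk r = 30% per dose, and a proportion q of reactors stopping after each event. The susceptible share shrinks by the factor (1 - r × q) at each dose, and the visit rate is s × r / (s + 1 - f), where s is the share still dosed. The rate is 3.0% at dose 1. At dose 8 it is 3.0% for q = 0, 1.8% for q = 25% and 1.0% for q = 50%. The result depends on q, which the documents do not give.

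**5. Denominator in 16.7.2.** With about 150 of 165 subjects contributing late (protocol 4.1), 8 reactors are 8/150 = 5.3% of those with data or 8/165 = 4.8% of the group. The gap is small, but the reader should know which is meant.

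**6. Percentage change in FEV1.** Protocol 7.5.4 requires absolute and percentage change by visit. SAP 16.7.1 plans only absolute values and change, although SAP 6.6 defines percentage change and the 20% and 30% thresholds are percentage changes.

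**The case against.** The SAP follows the protocol in working by visit, safety is descriptive, and no stated analysis is invalid. Systemic allergic reactions are events of special interest and are counted once per subject, so clinically important reactions are not seen only in by-visit columns. In the two arms that switch to placebo, the by-visit display is what separates active from placebo injections. SAP 8 leaves table format and content to templates that are not part of these documents, and an overall row might be there.

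Much of this stands, and it is why the by-visit tables should stay. It does not close the gap: the SAP text defines no per-subject derivation, and the adverse event tables use other scales. The missing percentage change is a departure from the protocol whatever the templates show.

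A reader might infer more than the documents support:
- **That later visits show mainly subjects who tolerated earlier doses.** Most first reactors continue, and many return to full volume. A model in which every reactor stops describes a rule the protocol does not contain.
- **That reactions spread evenly over eight columns.** In two active arms only four doses are active.
- **That both outcomes are counted among subjects with data.** Only the FEV1 section says so.

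**Conclusion.** The point holds as a gap in safety reporting. For FEV1 falls and injection-site grades, the plan has no summary of the share of subjects per regimen ever affected, or of the worst result per subject, and the by-visit counts cannot supply it. With k dosing visits at an equal rate and no missing data, the uncertainty is up to k-fold: 2% to 16% for an assumed 2% at each of eight visits. That range rests on assumed rates; the inability to recover subjects from visits does not.

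Early and late columns are not comparable, chiefly because of the placebo doses in two arms and the half doses, with some stopping. The size of any depletion is unknown, and no claim about it is made here. The unstated denominator in 16.7.2 and the missing percentage change in 16.7.1 follow from the text alone.

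No efficacy conclusion is affected. What is at stake is what the trial can say about tolerability by regimen, in particular at 20 nmol.

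**What to change.** Keep the by-visit tables and make these changes to the SAP:
- **16.7.1:** for each subject in the safety population, derive the worst percentage change in FEV1 from pre-dose to 30 minutes post-dose over Visits 3A-3D, 3E-3H and 3A-3H. Report n (%) with a fall above 20% and above 30% by treatment group, among subjects with at least one post-dose value in the range.
- **16.7.1:** restore the by-visit summary of percentage change in FEV1.
- **16.7.2:** add each subject's maximum grade for each of the four components over the same three ranges, on the same basis. The pre-dose inspection at a visit concerns the previous injection (protocol 6.2.2.1), so assign it to the dose that caused it.
- **16.7.2:** state the denominator for the by-visit percentages.

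The split at dose 4 matches the compliance summaries in SAP 14. The cost is a few lines of SAP text and two short tables from data already collected.

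Separately, protocol 4.6 (dosing ends) and 5.5.1 (withdrawal from the study) give different consequences for repeated local reactions. They must be reconciled, since this decides who has later data.

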#### **16.7.2. LOCAL REACTION AT INJECTION SITE**

Grading of each of the four components of an injection site reaction (pain, tenderness, induration/swelling and erythema/redness) is to be categorised as 'Grade 0', 'Grade 1', 'Grade 2', 'Grade 3' or 'Grade 4' in accordance with the severity of the reactions as specified in Table 7, Section 6.2.2.1 of the protocol.

Frequency (n) and percentage (%) of subjects with local reactions at the injection site are to be summarised by reaction grade and visit for each treatment group.

All injection site reactions are to be listed.

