#### Pre-dose assessments:

- Recording of any AEs.
- Recording of any changes to concomitant medication since last visit.
- Urine pregnancy test (for females and which must be negative for the subject to continue in the study).
- Examination of the injection site from previous administration (not relevant for Visit 3A) with recording of any injection site reaction on the following scale (FDA Guidance for Industry 2007) (Table 7):

	Grade 0	Grade 1	Grade 2	Grade 3	Grade 4
Pain	None	Does not interfere with activity	Repeated use of non-narcotic pain reliever >24 hours or interferes with activity	Any use of narcotic pain reliever or prevents daily activity	Emergency room visit or hospitalization
Tenderness	None	Mild discomfort to touch	Discomfort with movement	Significant discomfort at rest	Emergency room visit or hospitalization
Erythema/ Redness *	None	2.5 – 5 cm	5.1 – 10 cm	>10 cm	Necrosis or exfoliative dermatitis
Induration/ Swelling**	None	2.5 – 5 cm and does not interfere with activity	5.1 – 10 cm or interferes with activity	>10 cm or prevents daily activity	Necrosis

**Table 7** Grading of Injection Site Reactions

- Spirometry (FEV1) [asthmatic subjects should not take their  $\beta$  agonist asthma medication for a minimum of 4 hours prior to spirometry]. FEV1 must be  $\geq$ 70% of predicted for a subject to be dosed.
- In the event that the FEV1 is less than 70% of predicted the subject's asthma medication use should be reviewed and any appropriate adjustments made. The dosing visit should then be rescheduled within 5 days. A dosing visit may only be rescheduled once, after which time it becomes a missed visit.
- Vital signs (seated or semi-recumbent).
- Blood sample for biomarker analysis (OPTIONAL sub-study ONLY at Visit 3A see Section 6.4.4.7)

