#### Post-dose assessments:

- Spirometry (FEV1) will be performed 30 minutes after injection. Asthmatic subjects should not take their asthma medication for a minimum of 4 hours prior to spirometry.
- Vital signs measured 30 minutes after injection (seated or semi-recumbent).
- Examination of the injection site between 30 minutes after injection, with findings recorded using the scale above.
- Blood sample for tryptase will be taken only in the event of a suspected anaphylactic response. The initial sample should be taken approximately 1 hour after the attack, with a further sample at approximately 3 hours and then repeated every 3 hours until the Investigator is satisfied that the subject may be discharged. Note: blood sampling

VERSION FINAL4.0 CONFIDENTIAL PAGE 50 OF 92

\* In addition to grading the measured local reaction at the greatest single diameter, the measurement should be recorded as a continuous variable. \*\* Induration/Swelling should be evaluated and graded using the functional scale as well as the actual measurement.

**for tryptase must not delay initial resuscitation**. Any subject that experiences a suspected anaphylactic reaction must also have a sample collected for assay of tryptase at the next dosing visit or the end of study visit.

- Recording of any AEs prior to discharge.
- Issue new pDiary prior to discharge and instruct subjects to record details of injection site reactions in the 7 days after each dose.

Post-treatment assessments made within  $\pm 5$  minutes of the nominal times will not be regarded as a protocol deviation. Where more than one assessment is scheduled at a nominal time, the assessments will be conducted in the following order:

- 1. Vital signs
- 2. Spirometry (FEV1)
- 3. Examination of injection site

Subjects will be asked to complete a pDiary from Visit 3A to Visit 3I of AEs and concomitant medications. The pDiary will be checked at all visits and information entered into the eCRF. The pDiary must then be retained in the Investigator Site File.

The Investigator will assess the need for any asthmatic subject to be provided with a salbutamol/albuterol inhaler and/or peak flow meter at Visit 3A before leaving the clinic.

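### Injection-site erythema, and induration that does not interfere with activity, has no grade between 0 and 2.5 cm, and SAP 16.7.2 tabulates grades only

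*SAP*

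**What the plan says.** Protocol Section 6.2.2.1, Table 7, grades pain, tenderness, erythema/redness and induration/swelling from 0 to 4. For erythema and induration, Grade 0 is the absence of any reaction. Grade 1 erythema runs from 2.5 to 5 cm. For induration:

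- Grade 1: "2.5 – 5 cm and does not interfere with activity"
- Grade 2: "5.1 – 10 cm or interferes with activity"
- Grade 3: ">10 cm or prevents daily activity"

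Two footnotes follow. The single-asterisk one, marked on the erythema row, reads: "In addition to grading the measured local reaction at the greatest single diameter, the measurement should be recorded as a continuous variable". The double-asterisk one, on the induration row, reads: "Induration/Swelling should be evaluated and graded using the functional scale as well as the actual measurement".

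SAP 16.7.2 assigns each component to Grades 0 to 4 "in accordance with the severity of the reactions as specified in Table 7, Section 6.2.2.1 of the protocol". It then specifies the output: "Frequency (n) and percentage (%) of subjects with local reactions at the injection site are to be summarised by reaction grade and visit". It adds: "All injection site reactions are to be listed". It gives no rule for a reaction under 2.5 cm and no summary of the diameter. Protocol 7.5.4 plans a summary of local reactions by type and visit and does not mention diameter.

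**The concern.** The grade table is the only summary that SAP 16.7.2 specifies for local reactions, and its low end is undefined. An investigator who sees 1.5 cm of redness 30 minutes after an injection can record it as no reaction, although it is visible. The investigator can also record Grade 1, although it is below the Grade 1 limit, or leave the grade blank. The count of subjects with a local reaction then depends partly on which habit a site adopts.

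This bears on a stated purpose of the trial. Protocol 1.3.1 justifies the 20 nmol arm partly by asking whether its safety and tolerability match those of 12 nmol. Local reactions are a named safety parameter, and protocol 7.5.4 plans no inferential safety tests, so descriptive tables carry the comparison. There are up to eight injections per subject, so the ambiguity can recur at every dosing visit. The protocol already requires a measurement that would resolve it, at least for erythema. By contrast, SAP 16.5 and 16.7.1 give vital signs and FEV1 numerical summaries by visit and arm.

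**Working it through.** The plan states no figure on this point, so there is nothing to reproduce. The check has two parts.

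**1. Which diameters have no grade?** The erythema and induration rows of Table 7 were written as rules and applied to diameters from 0 to 13 cm in steps of 0.1 cm.

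| Component | Ungraded values at the low end |
|---|---|
| Erythema | 0.1 to 2.4 cm (24 of 24 grid values) |
| Induration, no interference with activity | 0.1 to 2.4 cm (24 of 24) |
| Induration that interferes with activity | none (at least Grade 2 at any size) |
| Induration that prevents daily activity | none (Grade 3 at any size) |

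There is also a hairline gap between 5.0 and 5.1 cm. It matters only if diameters are recorded more finely than 0.1 cm.

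**2. What would the grade table show?** The documents give no diameters, so this is an illustration on assumed values. Take mean diameters of 1.0 cm in one arm and 2.0 cm in another, normally distributed, with an SD of 0.5 or 1.0 cm. Negative values count as no reaction.

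If sites enter every reaction under 2.5 cm as Grade 0, the share at Grade 1 or above is P(Z ≥ (2.5 − mean)/SD):

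- SD 0.5: P(Z ≥ 3) = 0.1% against P(Z ≥ 1) = 16%
- SD 1.0: P(Z ≥ 1.5) = 7% against P(Z ≥ 0.5) = 31%

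If sites enter every visible reaction as at least Grade 1, the share is P(Z > (0 − mean)/SD):

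- SD 0.5: P(Z > −2) = 98% against P(Z > −4) = 100% after rounding
- SD 1.0: P(Z > −1) = 84% against P(Z > −2) = 98%

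The same reactions therefore give a difference of about 16 or 2 percentage points (SD 0.5), or about 24 or 14 (SD 1.0), depending only on the entry habit. A summary of the diameters would show the 1.0 cm difference in every case.

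**The case against.** The strongest reply is that this is a small matter in a descriptive table, and much of it stands.

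- **Other routes remain.** All injection-site reactions are listed. Subjects note reactions in the paper diary for 7 days after each dose. The adverse event definition in protocol 6.4.1 is wide enough to include a visible reaction, and SAP 16.1 summarises treatment-emergent events by term, by severity and within 24 hours of a dose. A reader might infer that small reactions are lost from the trial. The documents do not support that: the gap is in the grade summary. The adverse event tables carry no size, however. Whether the listing shows diameter cannot be checked, because the output shells are not in the documents.
- **Induration is partly covered.** A reader might infer that all induration under 2.5 cm is ungraded. It is not: swelling that interferes with or prevents activity reaches Grade 2 or 3 at any size.
- **No protocol commitment is broken.** The explicit requirement for a continuous value is marked on the erythema row, and protocol 7.5.4 promises no diameter analysis. This is an omission in the SAP and does not contradict the protocol.
- **Site habit should not favour an arm.** The trial is double-blind with products identical in appearance and 1:1:1:1 allocation, so differing habits would be expected mainly to add noise. That answers a charge of bias. It does not answer the loss of resolution.
- **The scale is external.** The protocol attributes Table 7 to a 2007 FDA guidance, which is a fair reason to leave its grades alone. It is no reason to leave the recorded measurement unsummarised.

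**Conclusion.** The point holds as a minor one. Table 7 leaves erythema, and induration that does not interfere with activity, ungraded above 0 and below 2.5 cm. SAP 16.7.2 inherits the gap, has no allocation rule, and does not summarise the diameter that the protocol asks sites to record. The summary tables therefore blur differences between arms in small reactions.

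Its size cannot be stated, because it depends on the unknown share of reactions under 2.5 cm and on how sites entered them. A reader might infer that arms averaging 1.0 and 2.0 cm would look identical, with every subject at Grade 0. That would need almost no spread in diameters and a uniform habit of entering Grade 0. With the assumed SDs above, some of the difference still reaches the table.

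The effect stops at descriptive local tolerability. Efficacy is unaffected, and the low-end gap does not touch the dose-reduction and discontinuation rules, which use Grades 3 and 4 for injection-site reactions.

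**What to change.** Amend SAP 16.7.2 before unblinding:

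1. Leave Grades 1 to 4 as defined in Table 7.
2. Add a separate row, 'present, >0 to <2.5 cm', for erythema and for induration that does not interfere with activity. Derive it from the recorded diameter. State that a reaction in this row is not also counted under Grade 0 or Grade 1, and show the grade the site entered in the listing.
3. Add descriptive statistics of the recorded greatest diameter (erythema, and induration where measured) by treatment group and visit, with the per-subject maximum. Report the number of reactions with no recorded diameter.

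An SAP change is the realistic route. The protocol planned the clinical phase to end in Q4 2016 and SAP version 2.0 is dated 24 March 2017, so new grading instructions to sites may come too late to alter entries already made.

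The cost is one extra row and one extra descriptive table, with no new data collection. The limit is that both cover only reactions for which a diameter was recorded.
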